# 6.3. Appendix 3 Data Derivations Rule

# 6.3.1. Criteria for Potential Clinical Importance

## 6.3.1.1. Laboratory Values

Haematology				
Laboratory Parameter	Units	Category	Clinical Concern Range	
			Low Flag (< x)	High Flag (>x)
Haematocrit	Ratio of 1	12+ years	0.201	0.599
Haemoglobin	G/L	12+ years	71	199
Platelet Count	x109/L	1+ years	31	1499
While Blood Cell Count (WBC)	x10  /L	12+ years	1.1	

Clinical Chemistry				
Laboratory Parameter	Units	Category	Clinical Concern Range	
			Low Flag (< x)	High Flag (>x)
Calcium	mmol/L	3+ years	1.50	3.24
Creatinine	IU/L	12+ years		>5 x ULN
Glucose	mmol/L	1+ years	2.2	27.8
Potassium	mEq/L	3+ years	2.8	6.5
Magnesium	mmol/L	6+years	0.3	2.5
Phosphorus	mmol/L	3+years	0.32	
Sodium	mEq/L	0+ years	120	160
ALT	U/L	12+ years		>239
Creatine Phosphokinase	IU/L	12+years		>5xULN

Liver Function			
Laboratory Parameter	Units	Category	Clinical Concern Range
			High Flag (>x)
ALT/SGPT	U/L	High	3 x ULN
AST/SGOT	U/L	High	3 x ULN
AlkPhos	U/L	High	3 x ULN
T Bilirubin	µmol/L	High	1.5 x ULN

# 6.3.2. Study Period

Assessments and events will be classified according to the time of occurrence relative to the study intervention period.

**Pre-treatment** is defined as time prior to the first dose of study intervention.

Assessment/Event Date ≤ Study Treatment Start Date

**On-treatment** is defined as time from first dose to last date plus 182 days.

Study Treatment Start Date < Assessment/Event Date ≤ Date of Last Dose of Study Treatment + 182 days

**Post-treatment** is defined as any time post on-intervention window, i.e. > last dose date plus 182 days.

Assessment/Event Date > Date of Last Dose of Study Treatment + 182 days

Assessments collected on the date of randomization, for which there is no time of assessment will be considered pre-intervention.

Assessments will be considered on-treatment if the assessment start date is missing.

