Study Intervention Administration		Χ							Χ										A minimum of 2 hours observation post-injection (at randomization and at Week 26; V9).
Device deficiencies review		Χ							Χ										
Safety Assessments																			
Physical exam	Х	X							Χ							X	Х		Height to be measured at Screening (V1) only. Weight does not need to be collected at V9. At V2 and V9, physical examination to be performed prior to dosing.
Vital signs	Х	Χ		х			Х		Х	Х			Х		Χ	Х	Х		Temperature, systolic and diastolic blood pressure and heart rate.
12-lead ECG	Х	Χ	Χ						X	Χ						Х	Х		ECG must be performed and assessed pre-dose. Twelve-lead ECG central over-read

	Screening (Visit 1)a, d						Tı	reatn	nent	Peri	od						Withdraw	/Follow Up	Natas
Procedure	į.							1	Wee	k								Follow-up	
	l in	0	4	8	12	16	20	24	26					44	48	52	26 or 52	30/56	Notes
	ee e											-7 da							
	Sci	2a	3a	4 c	5a	6 ^b	7a	8 b	9a	10a	11a	12b	13a	14b	15a	16a	a, e	b, e	
																			values should be used at all visits with the exception of V2 and V9 where 12-lead ECG machine read values should be used.
SAE review	х	Х	Х	х	Х	Х	Х	Х	Х	Х	X	Х	Х	Х	Х	Х	х	х	Any SAEs assessed as related to study procedures or related to a GSK product will be recorded from the time a participant consents to participate in the study.
AE review		Х	Χ	Χ	Χ	Χ	Χ	Χ	Χ	Χ	Χ	Χ	Χ	Χ	Χ	Χ	Х	Х	,
Concomitant medication review (including INCS)		Χ	Χ	Х	Χ	Χ	Χ	Χ	Χ	Χ	Χ	Χ	Χ	Χ	Χ	Χ	Х	Х	
Efficacy Assessment																			
Assessment of endoscopic NP score	X	х			х		X		х		X		х		X	х	Х		For V2, the nasal endoscopy assessment may be performed up to 7 days prior to the clinic visit. Nasal endoscopy must occur prior to randomization. For all other visits the nasal endoscopy assessment must not exceed the protocol defined windows of ±7 days from the nominal study visit.
CT Scan	Х															Х	X		CT scan is mandatory unless not approved by local ethics committee or institutional review board. The first CT

	(Visit 1)a, d						Tı	reatn	nent	Peri	od						Withdraw	/Follow Up	
Procedure	Ξ		Week EW Visit Follow												Follow-up	No.4			
1 1000dail0	Screening	0	4	8	12	16	20	24	26	28				44	48	52	26 or 52	30/56	Notes
	ree				_						sit (±			1	1			1 .	

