8.4.1. Time Period and Frequency for Collecting AE and SAE Information

- All SAEs will be collected from the start of intervention (Day 1) until the follow-up visit at the timepoints specified in Table 1. However, any SAEs assessed as related to study participation (e.g., study intervention, protocol-mandated procedures, invasive tests, or change in existing therapy) or related to a GSK product will be recorded from the time a participant consents to participate in the study.
- All SAEs will be recorded and reported to the sponsor or designee immediately and under no circumstance should this exceed 24 hours, as indicated in Appendix 3. The investigator will submit any updated SAE data to the sponsor within 24 hours of it being available.
- All AEs will be collected from the start of intervention (Day 1) until the follow-up visit at the timepoints specified in Table 1.
- Medical occurrences that begin before the start of study intervention but after obtaining informed consent will be recorded as medical history/current medical conditions not as AEs.
- Investigators are not obligated to actively seek information on AEs or SAEs after conclusion of the study participation. However, if the investigator learns of any SAE, including a death, at any time after a participant has been discharged from the study, and he/she considers the event to be reasonably related to the study intervention or study participation, the investigator must promptly notify the sponsor.

NOTE: The method of recording, evaluating and assessing causality of AEs and SAEs and procedures for completing and transmitting SAE reports to GSK are provided in Appendix 3.

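### SAP 6.3.2: the date expressions contradict the written definitions, so an adverse event dated on, or imputed to, the first-dose date counts as pre-treatment

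*SAP*

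**What the plan says.** One rule covers two kinds of data. SAP 6.3.2 opens: "Assessments and events will be classified according to the time of occurrence relative to the study intervention period". It then gives each period in words and as a date expression.

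- Pre-treatment, in words, "is defined as time prior to the first dose of study intervention"; the expression is "Assessment/Event Date ≤ Study Treatment Start Date".
- On-treatment, in words, "is defined as time from first dose to last date plus 182 days"; the expression is "Study Treatment Start Date < Assessment/Event Date ≤ Date of Last Dose of Study Treatment + 182 days".
- Post-treatment is any date after last dose + 182 days, and here words and expression agree.

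The only Day 1 tie rule concerns assessments: "Assessments collected on the date of randomization, for which there is no time of assessment will be considered pre-intervention". Events have no rule of their own.

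Two other sections bear on events dated Day 1. Protocol 8.4.1 states: "All AEs will be collected from the start of intervention (Day 1) until the follow-up visit". Occurrences between consent and first dose go to medical history, except SAEs related to study participation or a sponsor product, which are recorded from consent. SAP 6.3.6 lets imputed partial dates be used to place data in study phases. For an AE with start day and month missing, in the year of the first dose, the start is set to the intervention start date. The exception is an AE with a full stop date before the first dose, which is set to 1 January.

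**The concern.** The words and the expressions disagree on the first-dose date. The two signs are complementary (≤, then <), so a single misread character in the PDF is an unlikely cause. Including Day 1 in pre-treatment suits baseline assessments, which are largely made before dosing; for the ECG the schedule in Protocol 1.3 says "ECG must be performed and assessed pre-dose". It does not suit AEs, because an AE dated Day 1 is normally post-dose under Protocol 8.4.1.

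At stake are displays restricted to on-treatment events. The first-dose day includes at least two hours of post-injection observation (Protocol 1.3 and 6.4), so onsets that day are ones the trial sets out to capture. A year-only AE would be lost from those displays for a different reason: its imputed date falls on the excluded day, whenever in that year after the first dose it really began.

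**Working it through.** **1. Printed rule against the written definitions.** Take two doses 182 days apart: first dose Day 1, last dose Day 183, last dose + 182 = Day 365.

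| Event date | Printed expressions | Boundaries matching the words |
|---|---|---|
| Day -1 | pre | pre |
| Day 1 (first dose) | **pre** | **on** |
| Day 2 | on | on |
| Day 183 | on | on |
| Day 365 | on | on |
| Day 366 | post | post |

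Only the first-dose date changes class.

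**2. Window length.** Two doses: the printed window is Days 2 to 365 = 364 days; the corrected window is Days 1 to 365 = 365 days. The exposure formula in SAP 4.5.1 gives 182 + 182 = 364 days. One dose: 182, 183 and 182 days respectively. The printed window is therefore not short of the exposure formula. The issue is which day it includes.

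**3. Partial dates.** The 6.3.6 branch for a missing start day and month separates AEs that ended before the first dose (set to 1 January) from all others (set to the first-dose date). Under the printed ≤, both imputed dates are pre-treatment, so the branch makes no difference to phase assignment. With the event boundary corrected, the first group is pre-treatment and the second on-treatment. The imputation rule makes sense only with the corrected boundary.

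How many true onset dates, from first dose to year end, collapse onto the first-dose date depends on when dosing began. Illustrative first-dose dates in a non-leap year, two doses given:

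| First dose | Possible true onset dates in that year | Latest, days after first dose |
|---|---|---|
| 1 January | 365 | 364 |
| 1 April | 275 | 274 |
| 1 July | 184 | 183 |
| 1 October | 92 | 91 |

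The on-treatment window ends 182 + 182 = 364 days after the first dose, so every one of these true dates lies inside it. All become pre-treatment as printed. These are calendar dates, not expected event counts.

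The row for an AE with only the day missing cannot be read in the available text, so this step rests on the row for missing day and month.

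**4. Displays exposed.** On-treatment SAE row in 4.9: 1. AE overview by Region 2 in 4.10.1.2: 1. AEs by system organ class and preferred term in 4.10.1.2, by Age 1, Age 2, Sex, Race 1, Region 1 and Region 2: 6. Total 1 + 1 + 6 = 8.

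**5. Medications (SAP 6.1.4), a separate rule.** Post-treatment is printed as start date < last dose + 182 days. As printed:

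- every start before that date is post-treatment, including those already classed as on-treatment;
- a start on or after that date falls in no period;
- a start on the first-dose date is post-treatment only, though this last result depends on the strict on-treatment bounds, which may be an extraction artefact.

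The direction of the post-treatment sign does not depend on strict versus non-strict bounds, and the post-treatment line in 6.3.2 uses >.

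**The case against.** The best defence is that 6.3.2 already shows its intent. It classifies by time of occurrence, its words put the boundary at the first dose, and its tie rule applies only where no time is recorded. A programmer using onset times would therefore class a post-dose Day 1 event as on-treatment. The SAP also defers to the sponsor's core data standards and to the Programming Specifications, neither of which is available here, and these may settle the matter. That stands as a limit on certainty: the text conflicts, but no table is shown to be wrong. It does not help imputed dates, which carry no onset time, and the documents do not say whether AE onset time is collected.

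The harm may also be small. The main AE tables (4.5.2) and special-interest tables (4.5.2.1) state no period limit. In 4.9 only the SAE row is labelled on-treatment, and that section says its AE results come from 4.5.2.1. AE review is scheduled at most four weeks apart during treatment and SAEs are reported within 24 hours, so a year-only date should be rare, and for an SAE remote. All of this stands. It limits the size of the problem without removing the contradiction.

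Finally, the medication rule concerns different data, and symbols are visibly lost elsewhere in the SAP text (the age categories in Table 1, the minus signs in 6.3.3). That is a fair reason to treat 6.1.4 as a separate correction and to confirm its strict bounds, but a lost equality bar would not reverse the post-treatment direction.

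**Conclusion.** The concern holds and should be fixed. Two of the three date expressions in SAP 6.3.2 contradict their own definitions. The effect is confined to one date: an event on, or imputed to, the first-dose date is pre-treatment as printed and on-treatment according to the words, unless it began before the dose that day. Eight on-treatment safety displays are exposed. The main AE and special-interest tables keep these events as written, and no efficacy result changes. The reversed sign in 6.1.4 affects only the concomitant-medication summaries.

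The conclusion on displays assumes programming by date as printed, with nothing in the Programming Specifications or core data standards to override it. The number of affected events cannot be derived from the documents.

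**What to change.** In SAP 6.3.2 give events their own lines:

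- pre-treatment: event date < first-dose date;
- on-treatment: first-dose date ≤ event date ≤ last-dose date + 182 days;
- post-treatment: event date > last-dose date + 182 days.

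Use onset time on Day 1 where it is collected, and apply the same date rule to imputed dates. Keep the present pre-dose rule for Day 1 assessments. Leave the 4.5.1 exposure formula as it is, and note that the event window is one calendar day longer.

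Separately, in SAP 6.1.4 change post-treatment to start date > last dose + 182 days, and confirm that the on-treatment bounds are meant to be inclusive.

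The cost is SAP wording and programming flags. No new data are needed.

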## 6.3.3. Study Day and Reference Dates

The safety reference date is the study intervention start date and will be used to calculate study day for safety measures.

The efficacy reference date is the date of randomization and will be used to calculate study day for efficacy measures and baseline characteristics, as well as efficacy durations.

The study day is calculated as below:

- Assessment Date = Missing → Study Day = Missing
- Assessment Date < Reference Date → Study Day = Assessment Date Ref Date
- Assessment Data  $\geq$  Reference Date  $\rightarrow$  Study Day = Assessment Date Ref Date + 1

#### 6.3.4. Assessment Window

#### 6.3.4.1. Visit Based Assessments

No assessment windows are defined for visit based assessments. Nominal visits will be used for all reporting and analysis. Further details on the mapping of unscheduled visits are provided in the Programming Specifications document.

#### **6.3.4.2.** Daily Diary

Participants are to complete a daily diary assessment each morning. Table 2 below displays which daily diary records are included for each analysis time period. Any daily diary data collected post the 52-week time period will not be included in the Weeks 49-52 analysis of diary data.

Table 2 Daily Diary Assessment Windows

Analysis for A	M Measures		
Beginning Timepoint (Day)	Ending Timepoint (Day)	Analysis Time Period	
-27	1	Baseline	
2	29	Weeks 1 – 4	
30	57	Weeks 5 – 8	
58	85	Weeks 9 – 12	
86	113	Week 13 – 16	
114	141	Weeks 17 – 20	
142	169	Weeks 21 – 24	
170	197	Weeks 25 – 28	
198	225	Weeks 29 – 32	
226	253	Weeks 33 – 36	
254	281	Weeks 37 – 40	
282	309	Weeks 41 – 44	
310	337	Weeks 45 – 48	
338	365	Weeks 49 – 52	

Note: There is no Day 0 in CDISC reporting. Days -27 to -1 are immediately pre-randomization and Day 1 is the day of randomization (Visit 2). For the baseline time period, all values from Day -27 to Day 1 will be included in the baseline average; however, there must be a minimum of 4 non-missing values from Day -6 to Day 1 inclusive in order to derive the baseline, otherwise it will be set to missing.

Note: For each 4-week post-baseline time period the average will only be derived if there are non-missing values for at least 4 days out of 7 in at least 3 out of 4 weeks, with at least 15 minimum values, otherwise it will be set to missing.

## 6.3.5. Multiple measurements at One Analysis Time Point

Unless otherwise specified, if there are multiple measurements reported under the same nominal visit and planned time, the value of the first assessment will be used in any derivation of summary statistics, all individual measurements will be presented in any data listings.

Participants having both High and Low values for Normal Ranges at any post-baseline visit for safety parameters will be counted in both the High and Low categories of "Any visit post-baseline" row of related summary tables. This will also be applicable to relevant Potential Clinical Importance summary tables.

# 6.3.6. Handling of Partial Dates

Element	Reporting Detail		
General	
 
Partial dates we displays.
 
However, whe temporary varidates may be specific analys.
 
Imputed partial onset or duration or elapsed time imputed dates.
 
	re necessary, display macros may impute dates as ables for sorting data in listings only. In addition, partial imputed for 'slotting' data to study phases or for its purposes as outlined below.  I dates will not be used to derive study day, time to on (e.g., time to onset or duration of adverse events), e variables (e.g., time since diagnosis). In addition, are not used for deriving the last contact date in I analysis dataset.	
Adverse Events		or AE recorded in the CRF will be imputed using the	
	Missing start day and month	If study intervention start date is missing (i.e. participant did not start study intervention), then set start date = January 1.  Else if study intervention start date is not missing:  If year of start date = year of study intervention start date, then  If stop date contains a full date and stop date is earlier than study intervention start date, then set start date = January 1.  Else set start date = study intervention start date.  Else set start date = January 1.	
	Missing end day  Missing end day and month	A '28/29/30/31' will be used for the day (dependent on the month and year).  No Imputation	

Element	Reporting Detail		
	Completely	No imputation	
	missing	'	
	start/end date		
Concomitant Medications/Medical		for any concomitant medications recorded in the CRF ed using the following convention:	
History	Missing start day	If study intervention start date is missing (i.e. participant did not start study intervention), then set start date = 1st of month.  Else if study intervention start date is not missing:  If month and year of start date = month and year of study intervention start date, then  If stop date contains a full date and stop date is earlier than study intervention start date, then set start date = 1st of month.  Else set start date = study intervention start date.	
	Missing start day and month	Else set start date = 1st of month.  If study intervention start date is missing (i.e. participant did not start study intervention), then set start date = January 1.  Else if study intervention start date is not missing:  If year of start date = year of study intervention start date, then  If stop date contains a full date and stop date is earlier than study intervention start date, then set start date = January 1.  Else set start date = study. intervention start date.  Else set start date = January 1.	
	Missing end day	A '28/29/30/31' will be used for the day (dependent on the month and year).	
	Missing end day and month	A '31' will be used for the day and 'Dec' will be used for the month.	
	Completely missing start/end date	No imputation	

## 6.3.7. Early PK Access Key Activities

Designated representative(s) may be unblinded for performing population PK, PKPD dataset preparation and draft PK, PKPD model development using scrambled (random reassignment of subject identification numbers) PK, PKPD unblinded datasets.

The PK and PKPD datasets will include information on PK concentration, actual dosing information, demographics (including race and ethnicity), vital signs, concomitant medications, antidrug antibodies, biomarkers (e.g. eosinophils and IL5 concentration) and laboratory information. No information on adverse event and efficacy will be included.

#### 6.3.8. Trademarks

Trad	emarks of the GlaxoSmithKline
	Group of Companies
None	

Trademarks not owned by the GlaxoSmithKline Group of Companies
Claxoonintintine Group or Companies
SAS

